## Section 1: Introduction

### Background, rationale, and study aim

With a prevalence of approximately 6% in Denmark, Gestational diabetes mellitus (GDM) is one of the most common medical conditions during pregnancy. GDM predisposes women and their offspring to a range of short- and long-term morbidities, including early onset type 2 diabetes (T2D) and cardiovascular disease. Evidence from the US Diabetes Prevention Program (DPP) suggests that intensive lifestyle interventions can reduce the risk of T2D among women with prior GDM. However, more knowledge is needed about how to effectively reduce the risk of diabetes through sustained behavioural interventions after delivery. The Face-it intervention is a complex health promotion intervention embedded in multi-level supportive environments and addressing the individual, family, and health care system levels. This randomised controlled trial seeks to demonstrate whether the Face-it intervention is superior to usual care in reducing diabetes risk and improve quality of life for mothers in the first year following a GDM-affected pregnancy by promoting physical activity, healthy dietary behaviours and breastfeeding through a focus on social support, motivation, self-efficacy, risk perception and health literacy. The primary outcomes are body mass index (BMI) and quality of life (SF-12 mental component).

For a further description of the background and rationale for the Face-it trial, please refer to the Face-it study protocol (2) and the paper describing the development of the intervention (3).

### Objectives and Hypotheses

#### The primary objectives

The primary objectives of this trial are to investigate the effect of the Face-it intervention compared to usual care on change in BMI and quality of life among women with prior GDM.

Hypotheses for the primary outcomes: We hypothesise that the Face-it intervention is superior to no intervention (the usual care group) in reducing BMI from baseline to follow-up (12 months after delivery). The null hypothesis is that women in the intervention group have the same change in BMI at follow-up examination as usual care. The alternative hypothesis is that there is a difference between the two groups. We further hypothesise that the Face-it intervention is superior to no intervention (the usual care group) in increasing quality of life measured with the SF-12 mental component score from baseline to follow-up (12 months after delivery). For this primary outcome, the null hypothesis is also that women in the intervention group have the same change in quality of life at follow-up examination as usual care.

#### Secondary objectives

Secondary objectives are to describe changes associated with the intervention for the secondary and tertiary outcomes listed below. Hypotheses for each outcome in terms of expected change in intervention group relative to the usual care group are indicated with +/-.

#### *Clinical*

Anthropometric measurements (e.g., body composition)

|                          |   |
|--------------------------|---|
| Waist circumference (cm) | - |
| Hip circumference (cm)   | - |
| Body fat%                | - |
| Weight loss%             | + |

*Metabolic*

Blood tests (venous samples), OGTT, blood pressure

|                                 |   |
|---------------------------------|---|
| Fasting glucose (mmol/L)        | - |
| 2-h Glucose (mmol/L)            | - |
| HbA1c (mmol/mol)                | - |
| Impaired Fasting Glucose        | - |
| Impaired Glucose Tolerance      | - |
| Fasting insulin (pmmol/L)       | - |
| 2-h insulin (pmmol/L),          | - |
| HOMA-IR                         | - |
| HOMA- $\beta$                   | - |
| Systolic blood pressure (mmHg)  | - |
| Diastolic blood pressure (mmHg) | - |
| Total cholesterol (mmol/L)      | - |
| HDL cholesterol (mmol/L)        | + |
| LDL cholesterol (mmol/L)        | - |
| Triglycerides (mmol/L)          | - |

*Behavioural*

|   |   |
|---|---|
| DQS-2017 score                                  | + |
| IPAQ-SF Walk (min/day)                          | + |
| IPAQ-SF Moderate to Vigorous activity (min/day) | + |
| Breastfeeding duration, (months)                | + |

*Quality of Life & Mental health*

|                                  |   |
|----------------------------------|---|
| SF12 physical component score    | + |
| Self-perceived health            | + |
| Perceived stress scale score     | - |
| WHO-5 percentage score           | + |
| General Anxiety Disorder (GAD-7) | - |

*Psychosocial*

|   |   |
|---|---|
| Social support for diet Encouragement Family scale                  | + |
| Social support for exercise Participation Family scale              | + |
| TSRQ Exercise self-regulation and motivation Autonomous scale score | + |
| General self-efficacy   | + |
| RPS-DD Perceived risk of getting diabetes, % high risk              | + |
| RPS-DD Made behaviour changes to change risk of diabetes, % Yes     | + |
| HLQ Domain 3 Actively engage my health                              | + |
| HLQ Domain 6 Ability to actively engage with healthcare providers   | + |

## Section 2: Study methods

### Trial design

Multicentre, randomised, two-arm parallel controlled trial consisting of a health examination 10–14 weeks after delivery (baseline V1) and 12 months after delivery (follow-up V2). Randomisation to intervention or usual care group is performed at baseline examination.

### Brief description of the intervention

For a further description of the intervention please refer to the Face-it study protocol and the paper describing the development of the Face-it intervention (2,3).

### Randomisation

Women with prior GDM are the unit of randomisation. Randomisation was stratified on Centres: Odense, Aarhus, Copenhagen sites, i.e. for each centre, random allocation is performed in a 2:1 ratio to the intervention (2/3 of participants) or usual care (1/3 of participants). Randomisation was in random blocks of sizes 6/9/12/15, which ensures that allocation to intervention or usual care is unpredictable for recruiters and that the cumulative ratio of participants included to intervention vs. usual care is close to 2:1 throughout the inclusion period at each hospital. Randomisation will not be based on stratification for baseline variables. Details of the randomisation method are held securely within the files of the statistician. The randomisation procedure was generated by a statistician ([name]) prior to the commencement of recruitment. The allocation sequence will be implemented using the REDCap (Research Electronic Data Capture) electronic system. The randomisation process is described in full within the clinical trial protocol (2).

### Blinding

Randomisation to either the intervention or usual care group will occur immediately after baseline data collection. Thus, allocation will be concealed from both the participant and the investigators until participation has been accepted, eligibility confirmed, and baseline data collected. Neither participants nor the investigators will be blinded to the participants' allocation status after this point.

### Sample size

Calculation of the projected sample size is based on individual changes in BMI among women with prior GDM after 12 months of follow-up. The mean changes are compared between the intervention and usual care group. We expect the mean change in the intervention group to differ by  $-1.0 \text{ kg/m}^2$  relative to the usual care group. The standard deviation of individual changes after 12 months is expected to be  $2.5 \text{ kg/m}^2$ . Based on a 2:1 randomisation procedure, a power of at least 80% and type 1 error of 5% (two-sided), a sample size of 225 will be required to detect such a difference in BMI. Assuming 30% of participants will be lost between baseline (after randomisation) and follow-up, we will need to include 322 women at baseline in the study. Because of the relatively long period (10–30 weeks) between recruitment and baseline and the exclusion of women with overt diabetes at baseline (before randomisation), we also assume that 30% of those agreeing to participate will withdraw before baseline data collection or be excluded (see section 4) before randomisation. We therefore need to recruit 460 women. For full details of the sample size calculation, please refer to Face-it trial protocol (2).

### Framework

Superiority trial. Please refer to section on objectives.

### Statistical interim analyses

No statistical interim analyses will be performed and no guidelines for terminating the trial early has been made.

## **Timing of final analysis**

The final analyses of the primary outcomes will be performed when the last participant has completed the follow-up examination 12 months after delivery. All analyses described in this document will take place after ended data collection, which will be after participants have finished their last health examination in all study centres (expected to be in June 2023).

## **Timing of outcome assessment**

The primary outcomes are measured at baseline (V1) and at follow-up examination (V2).

## **Section 3: Statistical principles**

### **Confidence intervals and p-values**

All relevant statistical tests will be based on two-sided p-values using a 5% significance level. P-values will be reported for estimates related to the primary outcome and secondary outcomes. Wald-based 95% confidence intervals will be given for all reported estimates.

**Primary outcomes:** We will employ a hierarchical testing procedure with two separate hierarchies (one hierarchy for each of the two primary outcomes) to control the type 1 error rate for tests. Thus, if a test fails to confirm a given hypothesis, all subsequent tests within the specific hierarchy will be considered as tertiary outcomes. If the null hypothesis is rejected at the  $\alpha$  level of 0.05 (two-sided), i.e., the p-value of the null hypothesis test is  $< 0.05$ , statistical significance will be claimed. In order for the results to be declared in accordance with the hypothesis, the size of the estimated mean effect of the primary outcome, its direction, and the 95% confidence intervals will be required to support the tested hypothesis.

**Secondary outcomes:** Secondary outcomes within the clinical, metabolic and behavioural domains will belong to the hierarchy for BMI. Secondary outcomes within the quality of life & mental health domain will be embedded in the Quality of Life (SF-12 mental component) hierarchy. We will control for multiplicity using the Holm-Bonferroni method.

**Tertiary outcomes:** These outcomes are considered descriptive/explorative meaning no definite inferences can be made. Therefore, we will not correct for multiplicity.

## **Adherence, protocol deviations and population sample**

### **Compliance**

Intervention compliance is defined in two degrees as:

1. Intended intervention activity dose compliance: 3 home visits and  $\geq 9$  contacts in the LIVA app.
2. Minimum intervention activity dose compliance:  $\geq 2$  home visits and  $\geq 1$  contacts in the LIVA app but  $< 3$  home visits and 9 contacts in the LIVA app.

### **Completers**

Participants who have participated in the follow-up health examination (V2) and who are not pregnant at V2 will be considered completers in relation to the primary outcome on BMI.

### **Item non-responders/partial completers**

Participants who have not participated in the follow-up health examination (V2) and are not pregnant at V2 but have contributed with questionnaire data on the primary outcome on quality of life and/or secondary/tertiary outcomes at V2, will be considered completers in relation to the secondary/tertiary outcomes.

### **Lost to follow-up**

Participants who do not participate in the follow-up health examination (V2) nor provide questionnaire data at V2 will be considered lost to follow-up in relation to the primary outcomes. Participants who are pregnant at the follow-up visit will also be considered as lost to follow-up and excluded from analyses.

### **Per Protocol**

Completers/partial completers in the intervention group are considered *per protocol* if they:

- Are not lost to follow-up
- Comply with the intended intervention activity dose defined a priori

Completers/partial completers in the intervention group are considered *partial per protocol* if they:

- Are not lost to follow-up
- Comply with the minimum intervention activity dose defined a priori

All completers/partial completers in the usual care group are considered per protocol.

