### **Protocol deviators**

All completers in the intervention group who are not considered as having fully or partially followed the protocol (i.e per protocol or partial per protocol).

Data related to measures of adherence will be presented for all completers, item non-responders and for per protocol completers and partial per protocol completers. The distribution of the outcome will be visually inspected using QQ-plots and histograms and if Gaussian distributed it will be presented as means and standard deviations; if not it will be presented as medians (25th and 75th percentiles).

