## Analysis methods

### *Analysis population*

The primary analysis is an intention-to-treat analysis (ITT) including all participants who will be analysed as randomised.

Prior to further analyses and unblinding, all variables will be inspected to detect outliers to identify potential data entry errors.

Descriptive statistics will be summarised by randomisation group (see Section 4, Baseline characteristics).

The intervention effect for the primary outcomes will be estimated as the difference in BMI by randomisation group adjusted for BMI at baseline as well as the difference in SF-12 mental component score by randomisation group adjusted for SF-12 mental component score at baseline analysed in mixed models. Intervention effect for secondary and tertiary outcomes will likewise be estimated as difference in the outcome by randomisation group adjusted for the outcome at baseline. Continuous outcomes will be analysed in mixed models with a random effect for hospital, categorical outcomes will be analysed in generalized linear mixed models (family binomial, link logit) with a random effect for hospital, and duration of breastfeeding will be analysed using Cox proportional hazards regression with robust variance estimates for clustering due to hospital.

Due to randomisation, baseline values will not be statistically tested between groups. Mean differences between the study groups will be analysed using analysis of covariance, adjusted for baseline levels. Study site will be included as a random effect in the mixed models. Sample size of the study was based to prove a difference in BMI of  $-1.0 \text{ kg/m}^2$  between the two randomisation groups ( $\text{SD } 2.5 \text{ kg/m}^2$ ,  $\alpha = 0.05$ , power 80%).

Between group differences will be null-hypothesis tested and presented with P-values. The following supplementary analyses are planned for the primary outcomes as well as the secondary and tertiary outcomes:

1. An analysis similar to the one described above but including the per-protocol analysis population only. We will carefully consider the findings from the ITT analysis when drawing conclusions based on the per-protocol analysis, including whether a potential statistically significant result of the per-protocol analysis may be due to selection or the intervention.

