2. A sensitivity analysis, including the ITT analysis population, assessing the impact of missing data for the primary outcome. This analysis will only be performed in the case of a loss-to-follow-up rate  $> 10\%$ , i.e., more than 10% of all participants are missing at V2.
3. A sensitivity analysis excluding participants reporting use of glucose lowering medication at baseline.
4. A subgroup analysis stratified according to baseline BMI i)  $<25\text{kg/m}^2$  and ii)  $\geq 25\text{kg/m}^2$ .
5. A subgroup analysis stratified according to i) partner participation (defined as having a partner participating in the baseline visit) and ii) no partner participation (defined as not having a partner participating in the baseline visit).

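### Does the one-sided dose filter in the supplementary per-protocol analysis call for an added complier-average estimate?

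*SAP*

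**What the plan says.** SAP Section 3, Compliance, sets two dose levels: an intended dose (3 home visits and at least 9 app contacts) and a minimum dose (at least 2 visits and at least 1 contact, short of the intended dose). Under Per Protocol, an intervention woman counts as per protocol only if she is not lost to follow-up and meets this condition: "Comply with the intended intervention activity dose defined a priori". Women at the minimum dose form a separate partial class. For the comparator, "All completers/partial completers in the usual care group are considered per protocol".

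SAP Section 5, Analysis population, makes ITT primary. The first supplementary analysis is "An analysis similar to the one described above but including the per-protocol analysis population only", so it uses the same model: baseline value of the outcome, with hospital as a random effect. The SAP adds a caution: "We will carefully consider the findings from the ITT analysis when drawing conclusions based on the per-protocol analysis". It names the doubt itself: a significant finding in this population might reflect who was selected and not what the programme did.

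The other four supplementary analyses concern missing data, glucose-lowering medication at baseline, baseline BMI and partner participation. On adherence, Section 3 (Protocol deviators) states: "Data related to measures of adherence will be presented for all completers". The same sentence extends this to item non-responders and to the full and partial per-protocol classes.

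**The concern.** Reaching three visits and nine contacts is decided after randomisation and may go with motivation, health or social circumstances that also affect weight and mental wellbeing. Removing the women who fall short from one arm only breaks the balance that randomisation gave. Adjusting for the baseline outcome and hospital removes only the part of the imbalance that those variables carry.

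The SAP raises the question of selection but plans little to answer it. None of the other four supplementary analyses concerns compliance. Baseline summaries are planned by completion status (Section 4, Withdrawal/loss to follow-up), not by dose reached. No effect estimate is planned for the partial class. A favourable per-protocol result could then be read as evidence that the intervention works in those who take it up, when part of it is selection. A complier-average causal effect, with randomisation as instrument, looks like the natural addition for the two primary outcomes.

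**Working it through.** **Inputs.** From SAP Section 2, Sample size: difference 1.0 kg/m², SD of change 2.5, 2:1 allocation, two-sided 5%, power at least 80%, 225 evaluable women (150 and 75), 30% loss. Assumed, because the SAP does not give them: the share *p* of intervention women reaching the intended dose, and the prognostic gap *g* between them and the other intervention women that remains after baseline adjustment.

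**The plan's own figure.** Usual-care n = (1.96 + 0.8416)² × 2.5² × (1 + 1/2) / 1.0² = 73.6, so 74, and 3 × 74 = 222 in total against the stated 225. Power at 150:75 is about 80%. 225 / 0.7 = 321.4, so 322, as stated.

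**Bias of the per-protocol contrast with no true effect.** Bias = -(1 - *p*) × *g*; SE = 2.5 × √(1/75 + 1/(150*p*)); rejection = Φ(-1.96 + |bias|/SE) + Φ(-1.96 - |bias|/SE).

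| *p* | SE | *g* = 0.5: bias, rejection | *g* = 1.0: bias, rejection |
|---|---|---|---|
| 70% | 0.378 | -0.15, 7% | -0.30, 13% |
| 50% | 0.408 | -0.25, 9% | -0.50, 23% |
| 30% | 0.471 | -0.35, 12% | -0.70, 32% |

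Simulation at *p* = 50% gave 9.5% and 23%. With *g* = 0 there is no bias and rejection is 5%. If the women who fall short have the better prognosis, the sign reverses. The SAP gives no SD for the SF-12 mental score, but a gap of the same size in SD units (0.5/2.5 = 0.2 SD) gives the same rejection rates.

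**What ITT already shows.** Assume 60% reach the intended dose, 20% only the minimum and 20% less.

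- Selection only (*g* = 0.5, intended dose against the rest): per-protocol -0.40 × 0.5 = -0.20; ITT 0.
- Effect only (-1.0 at either dose, 0 below): per-protocol -1.00; ITT 0.8 × -1.0 = -0.80.

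The ITT estimate therefore moves with the explanation.

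**What a complier-average estimate would add.** When usual care has no access to the intervention, it is in essence ITT divided by the share of compliers. At 80% reaching the minimum dose, the ITT half-width 1.96 × 2.5 × √(1/75 + 1/150) = 0.69 becomes 0.69/0.8 = 0.87. In 20,000 simulated trials per case, its test agreed with the ITT test in 99.8% (selection only) and 98.9% (effect only).

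**Whether comparing the two isolates selection.** Take compliance as at least the minimum dose, in the same 60/20/20 split.

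- Selection only: -0.20 against 0.00, a difference of -0.20.
- No selection, effects -1.0/-0.5/0: complier effect (0.6 × -1.0 + 0.2 × -0.5)/0.8 = -0.875; difference -0.125.
- No selection, effects -1.0/0/0: complier effect -0.6/0.8 = -0.75; difference -0.25.

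Dose response alone can thus produce a larger difference than selection. The SE of the difference is 0.25 × 2.5 × √(1/90 + 1/30 + 1/30 + 1/75) = 0.19, so the chance of detecting -0.20 is about Φ(0.20/0.19 - 1.96), or 18%.

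Setting the threshold at the intended dose does not rescue the comparison. With effects -1.0/-0.5/0 and no selection, the complier effect is -0.70/0.6 = -1.17 against a per-protocol -1.00, because the benefit at the minimum dose is credited to the intended-dose women.

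**The case for a change.** The strongest reply is that ITT and per-protocol results are on different scales and the SAP gives no rule for setting one against the other. If an effect of -1.0 is confined to intended-dose women, ITT would be -0.3, -0.5 or -0.7 at 30%, 50% or 70% compliance. With an ITT standard error of 0.354, the power to distinguish these from zero is 13%, 29% or 51%. A null ITT result beside a favourable per-protocol one could then be argued either way. A complier-average estimate puts ITT on the uptake scale for the price of a paragraph and two models, with no new data.

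The scale point stands, but the power point does not help. Dividing estimate and standard error by the same share leaves their ratio unchanged, so the complier estimate is as uninformative as ITT in those cases. The rescaling itself needs only the ITT estimate and the class shares, which the planned adherence reporting allows.

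The estimate also assumes no effect below the threshold. A woman with one visit and many contacts, or three visits and no contact, would be below the minimum. If 40% were below it and had an effect of -0.5, the estimate would be inflated by 0.5 × 0.4/0.6 = 0.33 kg/m². It would also rest on observed outcomes after an expected 30% loss.

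A second reply is that the class limits are loosely worded. The minimum class does not clearly place a woman with three visits and fewer than nine contacts, and Section 3 does not say how online or merged visits count. This is true, but it is missing detail. The Protocol deviators paragraph implies three classes that cover all intervention completers, and the SAP says the pandemic adaptations were logged. An analyst can settle both points before unblinding.

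**Conclusion.** The asymmetry is real, and it is inherent because usual care has no dose to filter on. Beyond the ITT comparison and adjustment for the baseline outcome, nothing planned addresses selection. On assumed gaps of 0.5 to 1.0 kg/m² and intended-dose shares of 70% to 30%, the spurious BMI difference would be 0.15 to 0.70 kg/m² and the rejection rate 7% to 32%. With no gap it would be nil. All of this falls on a supplementary analysis that the SAP already ties to ITT with a selection warning.

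No stated figure or rule is wrong, and the trial's conclusion on either primary outcome does not depend on the point. The added estimate would carry nearly the same test as ITT, need a debatable assumption, and give a comparison in which selection (-0.20) cannot be told from dose response (-0.125 to -0.25) at a standard error of about 0.19. Adding it is a matter of preference, and leaving it out is a fair trade-off.
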